## BACKGROUND AND RATIONALE

The 11th version of the *International Classification of Diseases* (ICD-11) (WHO, 2018), produced by the World Health Organization (WHO), includes two trauma-based disorders; PTSD and Complex PTSD. The description of PTSD in ICD-11 is simpler than that provided within the DSM-5. In contrast to the 20 symptoms spread across four symptom clusters in DSM-5, ICD-11 PTSD includes just six 'core' symptoms across three clusters, each of which is directly related to one's traumatic exposure: re-experiencing in the here and now (Re: 2 symptoms), avoidance (Av: 2 symptoms), and a sense of current threat (Th: 2 symptoms). Diagnosis of ICD-11 PTSD requires the presence of one symptom per cluster, plus evidence of functional impairment. CPTSD is a broader diagnosis that includes the core PTSD symptoms plus an additional set of symptoms that are collectively referred to as 'disturbances in self-organisation' (DSO). These symptoms are intended to capture pervasive psychological disturbances associated with traumatic exposure and are distributed across three clusters: affective (hyper-activation and hypo-activation) dysregulation (AD), negative self-concept (NSC), and disturbances in relationships (DR). A CPTSD diagnosis requires that the PTSD criteria be met in addition to endorsement of symptoms from each of the DSO clusters.

Evidence from clinical samples (Karatzias et al., 2017) as well as population-based samples (Karatzias et al., 2019) suggests that CPTSD is a more common condition than PTSD in the UK. Although comparisons between general populations and military populations are lacking, in a recently completed cohort study (n=178) of a veteran help-seeking population in Combat Stress, it was found that 56% met diagnostic criteria for CPTSD versus 14% who met criteria for PTSD (Murphy et al., 2020). Identifying effective interventions to treat veterans with CPTSD is therefore of paramount importance.

Nevertheless, CPTSD is a new condition and there are currently no validated treatments available to aid recovery from this debilitating condition. One recent meta-analytic review (Karatzias et al., 2019b) suggested that existing interventions, commonly used for PTSD, such as Cognitive Behavioural Therapy (CBT) or Eye Movement Desensitisation and Reprocessing (EMDR) can be less useful for CPTSD symptoms, if there is history of childhood trauma. It is now well known that high rates of childhood trauma are common amongst military samples (Murphy et al., 2018). It is also well established that veterans with PTSD appear to profit less from current 'gold standard' treatments for PTSD than other trauma populations (Bisson et al., 2007, Phelps et al., 2018). A recent study demonstrated significant heterogeneity in veteran's treatment response to a standardized 6-week residential treatment program for PTSD; 27.5% were treatment resistant with no decrease in PTSD symptom severity, and 45.7% had moderate improvements. These groups who responded poorly to standard treatment were characterised by having higher baseline levels of PTSD, higher levels of anxiety and depression, and combat experience (Murphy et al., 2018); which might denote presence of CPTSD. Similarly, a study of the effectiveness of an accredited PTSD outpatient treatment programme for Australian veterans showed that high levels of baseline PTSD and other psychological problems, depression, and guilt, were predictors of poor treatment outcome. Again, it is likely that the poor responders were suffering from CPTSD rather than simple PTSD. Finally, evidence on the usefulness of phased interventions, which has previously been advocated as the gold standard for CPTSD, has also been questioned (Mahoney et al., 2018).

Emerging evidence suggests that it is imperative that new treatments need to be developed and tested for CPTSD. Karatzias and Cloitre (2020) have proposed modular therapy as a new promising area of treatment enquiry for CPTSD and a new treatment protocol has been developed (Cloitre et al., 2019). The use of a flexibly applied multi-modular treatment approach is new to the trauma field signalling a treatment innovation and paradigm shift in research methodology. However, there is a good rationale for its application and a successful precedent in mental health that lays out a methodological road map for its testing. First, such approaches have been found to be more effective compared to use of full

standardised treatment protocols for conditions such as depression and anxiety (Daleiden et al., 2006). Second, modular therapies for depression and anxiety appear to have a second benefit for patients in that they tend to be shorter and so time and expense burdens on the patient (Weisz et al., 2012). Third and relevant to treatment uptake of evidence-based therapies, clinicians trained in a modular therapy versus those trained in disorder-specific manualized therapy (e.g. CBT for depression) showed improved attitudes about evidence-based practices (Borntrager et al., 2009). Moreover, clinicians reported greater satisfaction with modular treatments as compared to standard evidence-based treatments, and reported their assessment of them as more effective compared to usual care (unspecified), suggesting that modular treatments provide the “best of both worlds” with high ratings on both practitioner satisfaction and effectiveness (Chorpita et al., 2015). Modular therapy has never been tested in CPTSD before.

Until the ICD-11 proposed the distinction between PTSD and CPTSD in 2018, there was no way to reliably allocate trauma exposed help-seeking individuals to treatment tailored specifically to their needs. Those with complex presentations were subsumed within a general PTSD treatment population. This project provides the opportunity, for the first time, to evaluate the feasibility of delivering a tailored treatment programme for those veterans who meet the diagnostic criteria for CPTSD.

## **AIMS**

ICD-11 CPTSD is a new condition and there are currently no identified effective treatments to enable recovery from this debilitating condition. Identifying effective interventions to treat veterans with CPTSD is therefore of paramount importance. We have recently proposed in the research literature a new innovative person-centred treatment approach for CPTSD (i.e. modular therapy; Karatzias and Cloitre, 2020). Enhanced Skills Training in Affective and Interpersonal Regulation (ESTAIR) involves targeting the symptoms of CPTSD clusters sequentially using concrete modules (i.e. specific number of sessions targeting specific clusters of symptoms). This intervention has never been tested in a military population before.

The project will provide information on recruitment and acceptability of a new treatment for CPTSD. The following main research questions will be addressed as part of this pilot project:

- I. Is it feasible to recruit for a study on ESTAIR vs. TAU in military personnel during the study recruitment period?
- II. What is the retention rate in the study at the end of treatment and at 3-month follow-up?
- III. Are primary and secondary outcomes acceptable from participants?
- IV. Is the new ESTAIR protocol acceptable by people with CPTSD?

## **STUDY DESIGN**

To our knowledge, this is the first pilot trial in the world on the acceptability of modular therapy for veterans with CPTSD using a new treatment manual. The present study has been approved by Edinburgh Napier University (SHSC2686062).

A randomised trial design will be employed, adhering to the *Consolidated Standards of Reporting Trials* (CONSORT; Schulz, 2010). This study has been designed to confirm that we can successfully recruit and retain participants in a larger trial characterised by the same design parameters (e.g., allocation ratio, blind assessment, types of treatment and control

offered, multiple sites). The planned randomised pilot study is therefore a 28-month feasibility/pilot of a single site, single (rater) blind trial of ESTAIR (psychological intervention vs. treatment as usual (TAU) alone for the treatment of CPTSD using the ITQ as the primary outcome. In this study, participants will be randomly allocated to receive treatment as usual (TAU) or a psychological intervention (ESTAIR) to improve CPTSD symptoms.

### **Randomisation**

Participants will be randomly allocated to group to minimize bias. Block randomisation will be used to ensure balanced assignment to the intervention and comparison group. Randomly permuted blocks (based on 12 blocks with 4 subjects per block) will be used to reduce the risk of predicting group assignment and ensure equal groups sizes. Randomised lists will be generated using an online, closed-source, web service (<http://www.randomization.com/>). Randomisation will be completed by [name].

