### **Recruitment**

When entering Combat Stress' clinical service, veterans are offered a formal assessment by a member of the multi-disciplinary team (MDT). As part of this process, they complete various psychometric measures of health including the International Trauma Questionnaire (ITQ). All cases are discussed at a weekly case management meeting. The research assistant will be embedded within the clinical team at Combat Stress' treatment centre in Leatherhead, Surrey to facilitate recruitment for this study. Veterans meeting criteria for CPTSD on the ITQ and deemed ready for therapy by the MDT will be approached to participate in the study.

The following procedure will be followed to recruit participants for the study:

1. The research assistant will attend the case management meeting to screen veterans for eligibility for the study.
2. If eligible, the research assistant will approach potential participants by letter and will be sent the patient information sheet and consent form. This invitation will be followed up by telephone call by the research assistant to discuss questions about the study and to discuss participants' willingness to participate. At this meeting, it will be emphasised that participation is voluntary.

**Note:** Due to the COVID-19 pandemic, the patient information sheet and consent form letter will be sent to potential participants via email, and they will later receive a printed copy by post.

3. If willing to participate, participants will be asked to attend a one to one or on-line meeting with the research assistant. At this meeting they will be asked again if they have any questions about the study, sign the consent form and complete pre-treatment measures. All forms can also be returned via mail. Following this, they will be randomised to one of the two groups (TAU or ESTAIR).
4. The research assistant will then inform Combat Stress of the outcome so participants in the TAU or who opted out can be offered the standard treatment.

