## OUTCOME MEASURES

Outcomes are as follows: **(i)** Retention & data completion rates at weeks 25 weeks post-treatment and 12-week follow-up, on the primary outcome; International Trauma Questionnaire (Cloitre et al., 2018) and secondary outcomes: PHQ Depression (Kroenke et al., 2001), GAD Generalised Anxiety (Spitzer et al., 2006), AUDIT Substance Misuse (Saunders et al., 1993), and PHQ-15 Medically Unexplained Symptoms (Kroenke et al., 2002) **(ii)** 12-month recruitment rate; **(iii)** participant & clinical staff views on trial & intervention acceptability and suggested changes. Baseline information on demographics including age, gender, marital status etc., will be gathered to characterise the sample.

A range of assessments will be administered by the research assistant to test the acceptability of primary (PTSD and CPTSD) (i.e. ITQ) and secondary outcomes (depression, anxiety, alcohol use, and somatisation) (e.g. GHQ-12, AUDIT). Participants in both groups will be asked to complete these outcome measures at baseline, after 25-weeks post-treatment and then again after at a 12-week follow-up. The ITQ will be also completed by the ESTAIR group at the end of every module. In addition, data will be recorded on retention and DNA rate. The research assistant will be masked to group allocation to demonstrate to future funders this is achievable in a future trial.

**Note:** The ITQ will be completed by the therapist and participant at the end of every model. Due to feasibility concerns, the research assistant will not be masked to group allocation when collected measures at baseline, post-treatment, and follow-up. This is not expected to have any impact on outcomes as all primary and secondary outcome measures are self-report.

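### Constant blocks of 4 in one sequence let a recruiter who knows past allocations deduce a third of assignments, which leaves the ESTAIR–TAU comparison open to selection bias

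*Combined protocol and SAP*

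**What the plan says.** The Randomisation section gives a single block size and a purpose for it: "Randomly permuted blocks (based on 12 blocks with 4 subjects per block) will be used to reduce the risk of predicting group assignment". The blocks are also meant to "ensure equal groups sizes", so each holds two places per arm. On the source of the list it says "Randomised lists will be generated using an online, closed-source, web service", and the person who carries out randomisation is named (the name is removed from the public copy). No stratification, varying block size, withholding of the block size or procedure for releasing allocations is described.

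Study Design describes a "28-month feasibility/pilot of a single site, single (rater) blind trial of ESTAIR", so there is one sequence.

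Under Recruitment, "The research assistant will attend the case management meeting to screen veterans for eligibility for the study". The same assistant writes to and telephones candidates, holds the meeting at which consent and baseline measures are taken, and after randomisation, "The research assistant will then inform Combat Stress of the outcome". The Note under Outcome Measures adds that "the research assistant will not be masked to group allocation when collected measures at baseline, post-treatment, and follow-up". Before any approach, the multi-disciplinary team (MDT) must also judge the veteran ready to start therapy. That judgement is not in the inclusion list and has no stated criteria.

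**The concern.** The plan credits its blocks with a property that they do not have. When every block has four places, two per arm, the last place follows from the first three, and the third follows from the first two whenever those match. The research assistant has the past allocations from the recruitment role itself and the block size from the protocol. The assistant also has some control over when a veteran is called and when the consent meeting is booked. A recruiter who expects the next place to be TAU could, without any ill intent, delay one veteran or bring another forward.

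If that happened, the arms would differ in prognosis at entry. The Phase 2 analysis under Data Analysis regresses 25-week scores on a treatment indicator and names no baseline covariate, so an imbalance created at entry would pass into the estimated difference.

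**Working it through.** **Inputs.** Block size 4, 12 blocks and equal arms (Randomisation); one site (Study Design); target of 60, 30 per arm (Sample size). The plan gives no predictability figure to reproduce. The calculation assumes that the guesser knows the block size and all earlier allocations.

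**Length of the list.** 12 × 4 = 48 places. The target of 60 needs 60 / 4 = 15 blocks, so the stated list is 12 places short.

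**Certain allocations.** A block with two places per arm has 6 equally likely orders.
- Places 1 and 2 are never certain.
- Place 3 is certain when the first two match, which has probability 1/3.
- Place 4 is always certain.
- Expected number per block: 1/3 + 1 = 4/3. Share: (4/3) / 4 = 33.3%, which is 16 of 48 or 20 of 60.

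**Best guess.** Name the arm with more places left in the block, and guess at random on a tie.
- Probability correct by place: 1/2, 2/3, 2/3, 1.
- Sum: 17/6. Rate: (17/6) / 4 = 70.8%, which is 34 of 48 or 42.5 of 60. Simple 1:1 randomisation gives 50%.

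**What each figure needs.** Completed blocks cancel, so the arm behind in the running tally is always the arm with more places left in the current block. The 71% therefore needs only the tally. The 33% needs the block size as well.

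**Possible bias (illustration; the shift is assumed, not in the documents).** Suppose enrolment moves prognosis by ±η SD according to the predicted arm, whenever there is a prediction. Correct minus wrong predictions per block are 1/3 at place 2, 1/3 at place 3 and 1 at place 4. The sum is 5/3, or 5/12 = 0.417 per allocation. The two arms shift in opposite directions, so the expected bias is 2 × 0.417 × η = 0.83η:

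| η (SD) | Bias (SD) |
|---|---|
| 0.10 | 0.08 |
| 0.25 | 0.21 |
| 0.50 | 0.42 |

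**After the change.** Block sizes 4, 6 and 8 were drawn at random with equal probability and simulated for 60 participants. The guesser knows the set of sizes but not their order.

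| Scheme | Certain | Best guess correct |
|---|---|---|
| Constant 4 | 33.3% | 70.8% |
| Random 4, 6, 8 | about 2.4% (runs gave 2.3% to 2.5%) | about 68% |

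Varying the sizes removes nearly all certain deductions. It lowers the guess rate by only about 3 points, because the tally argument holds for any mixture of balanced blocks.

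**The case against.** The strongest reply is that the route to bias is narrow. Eligibility rests on the ITQ diagnosis and listed criteria at a weekly meeting. A letter or email, a telephone call, a consent meeting and baseline measures follow, and only then is the veteran randomised. The MDT therefore judges readiness several steps before a place in the sequence is filled. This stands for the MDT. It does not remove the research assistant's influence over the timing of calls and bookings. Randomising after baseline protects the baseline scores from knowledge of that person's own allocation, but does not prevent inference from earlier allocations.

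The person who randomises may be independent of recruitment. That would protect the list, but the deduction does not need the list.

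The figures are also conditional. The documents do not say that recruiting staff use the block size. They do print it, and nothing says it is withheld.

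A reader might infer more than the text supports:
- **That the MDT follows the sequence.** The text says only that Combat Stress is informed so that standard treatment can be offered. The Note on masking names only the research assistant and concerns the collection of measures.
- **That retention by arm is compromised.** Recruitment and retention are to be summarised as counts and percentages with no stated split by arm, and the progression rule pools everyone randomised.
- **That the weakness will pass to the full trial.** Study Design speaks of shared design parameters, but block size is not among its examples. Carry-over is possible, not stated.

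**Conclusion.** The point holds as a potential weakness that is cheap to reduce. A constant block of 4 in one sequence does not give the low predictability that the Randomisation section claims for it. For someone who knows the block size and the past allocations, 33% of assignments are certain and 71% can be guessed. The research assistant is placed to know both.

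Predictable here does not mean that every next arm is known: even in this worst case two allocations in three are not certain. Nothing in the documents shows that selection has occurred. The bias figures above depend wholly on an assumed shift, applied at every allocation where a prediction is possible.

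What is exposed is the ESTAIR–TAU comparison at 25 weeks. The pooled recruitment and retention aims, and the progression rule that rests on them, are little affected. Nor should 50% be read as the rate that varied blocks would restore: it stays near 68%.

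**What to change.** In the Randomisation section:
1. Replace the constant block of 4 with block sizes that vary at random, for example 4, 6 and 8.
2. Withhold the sizes and the sequence from the research assistant and the MDT, and keep them out of the protocol version that they use. Varying the sizes is not enough alone: a guesser who knows the set still has about 2.4% of places certain. Withholding removes the basis for such deductions, though not the guess from the running tally.
3. State that the next allocation is released only after eligibility, consent and baseline measures have been recorded and dated. The plan already follows this order, so the addition is the record and the release rule. It does not stop the timing of calls, but leaves a trail that can be checked.
4. Generate a list that covers the target of 60 under Sample size, since 12 blocks of 4 give 48.

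The cost is a short protocol change, a regenerated list and a dated log entry, with no extra visits or staff. The downside is that arm sizes may differ by a few participants if recruitment stops inside a block; with a largest block of 8, by at most 4.

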## **STUDY POPULATION AND RECRUITMENT**

Combat Stress received approximately 3400 veteran referrals across the UK between April 2018/2019. Based on a recently completed cohort study, it is predicted that about 1,900 will meet criteria for CPTSD. As such, potential participants will be recruited and screened via Combat Stress.

Potential participants will be drawn from those referred to the Southern Treatment Combat Stress Treatment Centre (Leatherhead). They will have completed a mental health assessment as part of the referral and registered with Combat Stress for treatment. Potential participants will meet criteria for CPTSD, as indicated by the ITQ completed during their initial assessment. All new referrals are discussed at a weekly case management meeting to determine eligibility based on the inclusion and exclusion criteria below:

### **Inclusion criteria**

- Adults (18 years or older) in the caseload of Combat Stress
- UK armed forces veteran
- Help-seeking for trauma related psychological distress
- Meets diagnostic criteria for CPTSD as measured by the ITQ
- Proficiency in English language
- Signed informed consent provided

### **Exclusion criteria**

- Severe psychotic disorder (defined by previous clinical diagnosis)
- Current alcohol or drug use disorder
- Serious cognitive impairment
- Planned concurrent additional treatment

### **Recruitment**

When entering Combat Stress' clinical service, veterans are offered a formal assessment by a member of the multi-disciplinary team (MDT). As part of this process, they complete various psychometric measures of health including the International Trauma Questionnaire (ITQ). All cases are discussed at a weekly case management meeting. The research assistant will be embedded within the clinical team at Combat Stress' treatment centre in Leatherhead, Surrey to facilitate recruitment for this study. Veterans meeting criteria for CPTSD on the ITQ and deemed ready for therapy by the MDT will be approached to participate in the study.

The following procedure will be followed to recruit participants for the study:

1. The research assistant will attend the case management meeting to screen veterans for eligibility for the study.
2. If eligible, the research assistant will approach potential participants by letter and will be sent the patient information sheet and consent form. This invitation will be followed up by telephone call by the research assistant to discuss questions about the study and to discuss participants' willingness to participate. At this meeting, it will be emphasised that participation is voluntary.

**Note:** Due to the COVID-19 pandemic, the patient information sheet and consent form letter will be sent to potential participants via email, and they will later receive a printed copy by post.

3. If willing to participate, participants will be asked to attend a one to one or on-line meeting with the research assistant. At this meeting they will be asked again if they have any questions about the study, sign the consent form and complete pre-treatment measures. All forms can also be returned via mail. Following this, they will be randomised to one of the two groups (TAU or ESTAIR).
4. The research assistant will then inform Combat Stress of the outcome so participants in the TAU or who opted out can be offered the standard treatment.

